**Secondary Outcome Measures:**

1. Questionnaire Scores: Assessment of dietary intake (FFQ), physical activity (IPAQ), sleep quality (PSQI), and psychological health (SCL-90).

**4. Statistical Analysis Plan**

**Sample Size:** 96 participants.

**Analysis Sets:** Per-Protocol (PP) set and Intention-to-Treat (ITT) set.

**Statistical Methods:** Data will be analyzed using SAS 9.3 software. Continuous variables will be presented as Mean  $\pm$  SD. Repeated measures ANOVA or mixed-effects models will be used to analyze changes in the primary outcome measures (MPs, microbiota, metabolomics, inflammation, biochemistry, blood routine, and InBody data) from baseline to Week 3 and Week 6, comparing the interaction between Group and Time. Significance level is set at  $p < 0.05$ .

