### **3.4 Randomization and Blinding**

**Randomization:** Participants will be stratified by gender and BMI. A computer-generated randomization list (SAS 9.3) will allocate subjects 1:1 to the two groups.

**Blinding:** Double-blind design. Both investigators and participants are blinded to group allocation.

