### **3.5 Study Procedures**

Visits occur at Baseline (Week 0), Mid-term (Week 3), and End-point (Week 6).

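### The planned Group x Time analysis of change specifies neither baseline adjustment nor the gender and BMI randomisation strata, so it is valid but less precise than the collected data allow

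*Combined protocol and SAP*

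**What the plan says.** Section 4 (Statistical Analysis Plan) gives the whole model specification in one sentence: "Repeated measures ANOVA or mixed-effects models will be used to analyze changes in the primary outcome measures", covering "MPs, microbiota, metabolomics, inflammation, biochemistry, blood routine, and InBody data", "from baseline to Week 3 and Week 6, comparing the interaction between Group and Time". No covariate is listed, and the choice between the two model families is left open.

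Section 3.4 (Randomization and Blinding) states that "Participants will be stratified by gender and BMI" and that a computer-generated list "will allocate subjects 1:1 to the two groups". The BMI cut-points are not given. Section 3.5 (Study Procedures) places visits at Weeks 0, 3 and 6, so a baseline value is available for outcomes measured at every visit.

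The size is given as "Sample Size: 96 participants", without an effect size, SD, power, dropout allowance or baseline to follow-up correlation.

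**The concern.** Two pieces of information already in hand have no stated role in the model.

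- **Baseline value.** The plan uses it only as the starting point of a change. Subtracting the whole baseline value is efficient only when baseline and follow-up are almost perfectly correlated. When the correlation is modest, subtraction adds noise; below r = 0.5 the change score varies more than the follow-up value alone. Single-sample measures such as fecal microplastics and cytokines could plausibly be in that range, but that is an assumption.
- **Randomisation strata.** Stratifying balances the arms on sex and BMI. If the model leaves those factors out, their variation stays in the residual, and the reported standard error does not reflect the balance achieved.

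At stake is precision in a trial of 96 people for which no power calculation is shown, so spare precision cannot be taken for granted.

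**Working it through.** **Inputs from the documents.** N = 96, allocated 1:1, so 48 per arm if all are randomised; visits at Weeks 0, 3 and 6; significance level 0.05 (two-sided assumed, as sidedness is not stated); strata gender and BMI.

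**Inputs assumed.** Correlation r from 0.1 to 0.98; equal variance s² at baseline and follow-up; complete data; a Week 6 difference of 0.577 SD, used for illustration only; strata explaining 10% or 25% of the variance of change.

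**The plan's own figure.** N = 96 cannot be reproduced, because nothing behind it is stated. For scale, 48 per arm detects (1.96 + 0.842) × √(2/48) = 0.57 SD with 80% power, in units of the SD of whatever quantity is compared.

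**Step 1: what the interaction estimates.** With baseline as an unconstrained repeated response and complete data, the Group by Time contrast at a visit is the difference between arms in mean change from baseline.

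**Step 2: variance per participant.**

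- Change: s² + s² − 2rs² = 2(1−r)s²
- Baseline-adjusted: (1−r²)s²
- Ratio, adjusted to change: (1−r²) / [2(1−r)] = (1+r)/2
- Fraction saved: 1 − (1+r)/2 = (1−r)/2

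| r (assumed) | Change, 2(1−r) | Adjusted, 1−r² | Saved | Adjusted N as precise as change at N = 96, 96(1+r)/2 |
|---|---|---|---|---|
| 0.1 | 1.80 | 0.99 | 45% | 53 |
| 0.3 | 1.40 | 0.91 | 35% | 62 |
| 0.5 | 1.00 | 0.75 | 25% | 72 |
| 0.7 | 0.60 | 0.51 | 15% | 82 |
| 0.9 | 0.20 | 0.19 | 5% | 91 |
| 0.98 | 0.040 | 0.0396 | 1% | 95 |

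If Weeks 3 and 6 are averaged and all pairs of visits share correlation r, the change variance is (1+r)/2 + 1 − 2r and the adjusted variance is (1+r)/2 − r². The saving is then 47% at r = 0.3, 33% at 0.5, 20% at 0.7 and 7% at 0.9. A second post-baseline visit therefore does not remove the loss.

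**Step 3: power, for illustration.** Two-sample t calculation for Week 6 alone, 48 per arm, difference 0.577 SD, no dropout:

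| r (assumed) | Change | Adjusted |
|---|---|---|
| 0.3 | 65.7% | 83.5% |
| 0.5 | 79.9% | 89.8% |
| 0.7 | 95.1% | 97.5% |
| 0.8 | 99.3% | 99.7% |

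At r = 0.9 both are about 100%.

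**Step 4: the strata.** Scale the variance of change to 1 and let the strata explain a share g of it. With arms balanced within strata, the true variance of the group difference is (1−g) × 2/48. A model without strata reports about 2/48 = 0.042. True type I error is therefore about 2[1 − Φ(1.96/√(1−g))].

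- g = 0.25: true variance 0.031, reported 0.042; 1.96/√0.75 = 2.26, giving about 2.4%. Simulation (four balanced sex by BMI cells) gave 2.3% to 2.5%, and about 5% with strata in the model.
- g = 0.10: 1.96/√0.90 = 2.07, giving 3.9%. Simulation gave 3.7% to 3.8%.

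Adding strata corrects the reported standard error; it does little to the true variance. In a simulation at r = 0.5 with strata explaining 25% of the outcome variance at each visit, the true variance of the change estimate was 0.0418 with or without strata. After baseline adjustment it fell only from 0.0289 to 0.0280. The savings in step 2 therefore belong to the baseline covariate.

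**The case against.** The strongest reply is that the plan is brief and silent: it excludes no covariates. A mixed model with a common baseline mean across arms fits its wording and would recover essentially all the gain. This stands as far as it goes. A reader might infer that the sponsor has decided against adjustment, and the documents do not show that. But the same sentence equally permits repeated measures ANOVA of change, which, followed as written, gives the less precise result.

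Other stronger readings are also unsupported:

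- **That the planned test is invalid or biased.** It is not. The contrast is unbiased under randomisation; a chance baseline imbalance matters only conditionally on having occurred. Omitting the strata makes the test conservative.
- **That a fixed share of precision, such as 15% to 35%, is lost on every outcome.** That range needs r between 0.3 and 0.7, and no document gives r. Stable outcomes such as weight, BMI and waist could plausibly have r of 0.9 or more, where 5% or less is at stake.
- **That the power figures describe this trial.** They are for one Week 6 comparison at an assumed effect. The plan tests an interaction over three time points and does not name Week 6 as the sole contrast.
- **That this is the largest precision gain available.** No alternative was compared.

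**Conclusion.** The point holds as a free improvement in precision and a gap in specification. The change contrast has a larger variance than the baseline-adjusted one for any r below 1. The saving ranges from about 45% (r = 0.1) to 1% (r = 0.98) of the change-contrast variance, and is therefore worthwhile for noisy outcomes and negligible for very stable ones. It rests on equal variances, complete data and an assumed r that will vary across the seven primary domains.

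The strata are a separate, smaller matter: the analysis should match the randomisation so that standard errors are correct. The cost of omission depends on how strongly change varies with sex or BMI, which the documents do not indicate.

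The algebra is certain; the size for any given outcome is not. The sponsor should make the change.

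**What to change.** For each scalar continuous outcome, replace the open choice of models with one specification:

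- a mixed model on the Week 3 and Week 6 values, with group, visit, group by visit, baseline value, baseline by visit, sex and the BMI randomisation stratum; or
- equivalently, a constrained longitudinal model with a common baseline mean, plus the two strata.

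Report the baseline-adjusted group difference with its 95% CI, and name the visit contrast of interest.

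Three details need attention. State the BMI categories used in randomisation, so that the model uses the same stratum. Where the outcome is BMI itself, do not also enter continuous baseline BMI as a second covariate, since it duplicates the baseline value. Metagenomic and metabolomic profiles are outside this model, except for scalar summaries such as diversity indices, and need their own specification.

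The cost is SAP wording only. Baseline values, sex and BMI are already collected, and no extra participants, visits or assays are needed. The wording should be fixed before unblinding, so that the choice of model cannot depend on the results.

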### **3.6 Outcome Measures**

#### **Primary Outcome Measures:**

1. Fecal microplastics (MPs) levels: Assessed by Py-GC/MS. Includes detection of 11 types of plastics (PC, PE, PP, PS, PA6, PET, PLA, PVC, PA66, PBAT, PMMA). Reported in µg/g dry weight.
2. Gut microbiota composition: Assessed by Fecal Metagenomics sequencing to analyze diversity and functional genes.
3. Blood metabolic profiles: Assessed by untargeted Blood Metabolomics to identify metabolic pathway alterations.
4. Inflammatory cytokines levels: Measurement of serum markers including MCP-1, IL-1β, IL-6, TNF-α, P-selectin, CRP, etc..

5. Blood biochemical indicators: Assessed by automatic biochemical analyzer. Includes liver function and blood lipid indicators (Total Cholesterol, Triglycerides, HDL, LDL).
6. Routine blood examination: Assessed by automatic blood cell analyzer. Includes white blood cell count (WBC) and five-part differential.
7. Anthropometric and body composition indicators: Measurement of body weight, BMI, waist circumference, hip circumference, body fat percentage, and muscle mass via Bioelectrical Impedance Analysis.

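### The SAP leaves the error structure of the three-visit analysis open; a single pooled error would make the Group x Time test slightly liberal and a Week 6 contrast more so, and one sentence would settle it

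*Combined protocol and SAP*

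**What the plan says.** Section 3.5 sets three equally spaced visits, at Weeks 0, 3 and 6, and calls the last one the end-point. Section 4 (Statistical Analysis Plan) states: "Repeated measures ANOVA or mixed-effects models will be used to analyze changes in the primary outcome measures". The changes are those "from baseline to Week 3 and Week 6", and the stated test is "comparing the interaction between Group and Time", at p < 0.05.

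The choice between ANOVA and mixed model is left open. Neither section 4 nor any other section gives random effects, a within-participant covariance structure, a sphericity correction, a degrees-of-freedom method or an error term for comparisons at a single visit. Neither Week 3 nor Week 6 is named as the primary time point. The sentence covers all seven primary outcome groups, including "Measurement of body weight, BMI, waist circumference, hip circumference, body fat percentage, and muscle mass via Bioelectrical Impedance Analysis".

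**The concern.** Classical repeated-measures ANOVA uses one within-participant error for every visit comparison. That is right only if the difference between any two visits has the same variance (sphericity). A mixed model whose only random effect is a participant intercept makes the same assumption. With two repeated levels the condition holds automatically; with three it can fail.

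If measurements six weeks apart agree less than measurements three weeks apart, the pooled error averages two smaller variances with one larger one. Applied to the Week 6 change, the average is too small: the confidence interval is too narrow and the test rejects too often. Applied to the Week 3 change, it is too large. This happens with complete data and does not depend on how dropouts are handled. The wording of section 4 permits both an analysis that holds its level and one that does not, and the choice could be made after the data are seen.

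**Working it through.** **Inputs from the documents.** Section 4 gives "96 participants" and section 3.4 says the list will "allocate subjects 1:1 to the two groups", so 96/2 = 48 per arm. Three visits (section 3.5). Level 0.05 (section 4); sidedness is not stated and is taken as two-sided.

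**Inputs assumed.** Between-visit correlations, SDs and drift are not in the documents, so a range is shown. Data are complete and normal, with no treatment effect.

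**Formulas.** Let v03, v36 and v06 be the variances of the within-person differences between the visits named.
- Pooled error: 2 x E[MSE] = (v03 + v36 + v06)/3.
- Ratio for Week 6: R = v06 / [(v03 + v36 + v06)/3]. The pooled SE is 1/sqrt(R) of the true SE.
- Actual size: 2[1 - Phi(1.96/sqrt(R))]. For Week 3, put v03 in the numerator of R.
- AR(1) with three-week correlation r: R = 3(1 + r)/(3 + r).
- Random slopes, with s = slope variance per three-week interval divided by residual variance: R = (1 + 2s)/(1 + s).

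**Nominal level first.** With equal correlations R = 1 and the size is 5.0% (simulated 4.98%), so the pooled test meets the stated level when its assumption holds.

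**Worked cases.**
- Random walk: v03, v36, v06 = 1, 1, 2; mean 1.333; R = 1.5; SE ratio 0.816 (18% too small); size 2[1 - Phi(1.600)] = 11.0%. Week 3: R = 0.75, size 2.4%.
- AR(1), r = 0.7: variances 0.60, 0.60, 1.02; mean 0.74; R = 1.378; size 9.5%.
- Weeks 3 and 6 more alike than either is to baseline (correlations 0.5, 0.5, 0.8): v03 = v06 = 1.0, v36 = 0.4; mean 0.8; R = 1.25; size 8.0% at both visits. Here Week 3 is liberal too.

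**Range.** The simulated columns use 100,000 null trials per row, 48 per arm.

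| Assumed pattern | R, Week 6 | Week 6, formula | Week 6, simulated | Week 3, formula | Uncorrected Group x Time F, simulated |
|---|---|---|---|---|---|
| Equal correlations | 1.00 | 5.00% | 4.98% | 5.00% | 4.95% |
| AR(1) 0.3 | 1.18 | 7.14% | 7.03% | 3.98% | 5.02% |
| AR(1) 0.5 | 1.29 | 8.39% | 8.34% | 3.43% | 5.31% |
| AR(1) 0.7 | 1.38 | 9.50% | 9.49% | 2.95% | 5.55% |
| AR(1) 0.95 | 1.48 | 10.73% | 10.68% | 2.45% | 5.81% |
| Random walk | 1.50 | 10.95% | 11.08% | 2.36% | 5.99% |
| AR(1) 0.9, 20% of variance visit noise | 1.16 | 6.85% | 6.95% | 4.11% | 5.18% |
| AR(1) 0.9, 5% visit noise | 1.33 | 8.90% | 8.93% | 3.20% | 5.58% |
| Random slopes, s = 0.5 | 1.33 | 8.96% | 8.99% | 3.18% | 5.47% |
| Random slopes, s = 2 | 1.67 | 12.90% | 12.91% | 1.64% | 6.57% |
| Random slopes, s = 100 (near-pure) | 1.99 | 16.47% | 16.77% | 0.58% | 8.49% |

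As s grows, R tends to 2 and the Week 6 size to 16.6%.

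**With the alternative.** Over all simulated patterns, a Week 6 test using the error of the Week 6 change itself ran at 4.9-5.1%. The Group x Time test with unstructured covariance ran at 4.9-5.2%, and the Greenhouse-Geisser corrected F test at 4.7-5.1%.

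**The case against.** A reader might infer that the SAP commits to a pooled-error test and that false positives at Week 6 will therefore roughly double. The documents do not support that, for four reasons.

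1. **The model is open.** Section 4 offers mixed models as an equal alternative and nowhere limits them to a participant intercept. It also does not rule out a corrected ANOVA. Versions that hold about 5% fit the same sentence. This stands: the gap is under-specification.
2. **The named test is the interaction.** No Week 6 contrast is prespecified, and the uncorrected interaction F test is only mildly affected. This stands for the formal test. But a two-degree-of-freedom F test gives no effect size, so reporting the changes that section 4 describes requires a standard error for each visit, and that is where a pooled error does most harm.
3. **Drift is not documented.** No section gives a correlation. Treatment lasts 42 days and recent weight change above 5% is an exclusion, which gives some reason to doubt strong drift in weight. Outcomes with substantial visit noise fall nearer 6-9%. This stands, so every inflated figure is conditional.
4. **The response may be the change score.** With changes to Weeks 3 and 6 as the response there are only two repeated levels, sphericity is automatic and the three-visit formula does not apply. Section 4 can be read this way. A variance pooled over the two changes could still be wrong for Week 6, though by a different amount. That the reading cannot be settled from the text is a further reason to specify the model.

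**Conclusion.** The point holds in conditional form. If a single pooled error is used over three visits, and visits further apart agree less:

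- the Group x Time F test runs at about 5-6% under AR(1) to random-walk drift, and at up to about 8.5% with near-pure random slopes;
- a Week 6 change-from-baseline contrast runs at about 7-11%, staying at 5% if correlations are equal and exceeding 11% only with strong random slopes;
- a Week 3 contrast is conservative, at about 4% down to 2.4%, over AR(1) to random-walk drift.

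These figures rest on assumed correlations, 48 per arm, complete normal data and a two-sided 5% level. They show what the wording permits, not what the trial will do. The point is a free improvement: the plan is not wrong as written, but it leaves open a choice that a better-specified method closes.

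**What to change.** For the continuous outcomes, delete the repeated-measures ANOVA option from section 4 and specify: a linear mixed model with visit as a categorical factor, group, and Group x Visit; an unstructured within-participant covariance matrix (in SAS, PROC MIXED with REPEATED and TYPE=UN); REML; and a small-sample degrees-of-freedom method such as Kenward-Roger. Take the Week 3 and Week 6 between-group contrasts in change from baseline, with their confidence intervals, from that model. State beforehand what is done if it does not converge; a structured fallback brings back part of the assumption. If ANOVA is kept as a sensitivity analysis, use the Greenhouse-Geisser correction for the interaction and contrast-specific errors for visit comparisons.

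The cost is one or two sentences of SAP wording. A three-visit unstructured matrix has six parameters (three variances, three covariances), which 96 participants can support, and the SAS 9.3 named in the SAP can fit it. Little is lost if correlations really are equal. The change does not by itself name a primary contrast, or settle the scale for skewed outcomes or the analysis of high-dimensional data such as metagenomics and metabolomics.

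### The only planned comparison, Group by Time, is not tied to Week 6 and may be run by either of two methods in either of two unranked analysis sets

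*Combined protocol and SAP*

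**What the plan says.** Section 4 gives the method in one sentence: "Repeated measures ANOVA or mixed-effects models will be used to analyze changes in the primary outcome measures". The comparison covers changes "from baseline to Week 3 and Week 6, comparing the interaction between Group and Time". No rule is given for choosing between the two methods, and the coding of Time is not stated. A threshold of 0.05 follows, without sidedness.

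The analysis sets are listed as "Per-Protocol (PP) set and Intention-to-Treat (ITT) set". Neither is defined or named as primary, and no method for missing data is given.

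Section 3.5 sets the schedule: "Visits occur at Baseline (Week 0), Mid-term (Week 3), and End-point (Week 6". No section states a primary time point, a between-group contrast at Week 6 or an effect estimate to be reported.

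**The concern.** With two groups and three categorical visits, the Group by Time interaction asks whether the arms' profiles differ anywhere over Weeks 0, 3 and 6. A difference present only at Week 3 answers that question as well as one present at Week 6. A reader of the results would probably want to know whether the arms differ at the end of the six-week intervention, and the named test does not address that directly. It may also spend power on a second degree of freedom.

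The method and the set are open too. Conventional repeated-measures ANOVA needs all three visits from each participant. If that option is taken and visits are missed, an analysis labelled ITT is really one of completers. Two methods and two sets give 2 x 2 = 4 routes to each p-value. Selecting completers or adherent participants can bias the randomised comparison if the reasons for missing data differ by arm.

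**Working it through.** **Inputs from the documents.** Total size "96 participants" (Section 4); the list will "allocate subjects 1:1 to the two groups" (Section 3.4), so n = 48 per arm; three visits (Section 3.5); threshold 0.05 (Section 4), taken here as two-sided for t tests.

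**Assumptions, because the documents are silent.** Effect 0.5 SD, SD equal at all visits, correlation r between any two visits (compound symmetry), Time categorical. The sample size of 96 comes with no effect size, SD, power or dropout, so it cannot be reproduced. A two-group comparison with 48 per arm has 80% power for about 0.57 SD, but that is back-solved and not a figure in the plan.

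**Step 1: degrees of freedom.** (2 - 1) x (3 - 1) = 2.

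**Step 2: the interaction test.** Let a and b be the group effects at Weeks 3 and 6 in SD units. Under compound symmetry the noncentrality is

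lambda = n(a² - ab + b²) / [3(1 - r)], referred to F on 2 and 93 df.

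- Vanished effect (a = 0.5, b = 0): a² - ab + b² = 0.25.
- Sustained effect (a = b = 0.5): also 0.25, so the power is identical.
- Building effect (a = 0.25, b = 0.5): 0.0625 - 0.125 + 0.25 = 0.1875.

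At r = 0.5, lambda is 48 x 0.25 / 1.5 = 8.0 for the first two and 48 x 0.1875 / 1.5 = 6.0 for the third. At r = 0.3 the values are 5.71 and 4.29.

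**Step 3: the Week 6 contrast.** Baseline-adjusted: b / sqrt[(1 - r²) x 2/n], which at r = 0.5 is 0.5 / sqrt(0.75 x 2/48) = 2.83. Change score: b / sqrt[2(1 - r) x 2/n] = 2.45 at r = 0.5. Unadjusted Week 6 value: b / sqrt(2/n) = 2.45 at any r.

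| r | Interaction, vanished or sustained | Interaction, building | Week 6 change score | Week 6 baseline-adjusted |
|---|---|---|---|---|
| 0.3 | 55% | 43% | 54% | 72% |
| 0.5 | 70% | 57% | 68% | 80% |
| 0.7 | 91% | 80% | 88% | 92% |
| 0.8 | 98% | 94% | 97% | 98% |

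The Week 6 columns depend only on b = 0.5, so they apply to both the sustained and the building effect. For the vanished effect a Week 6 contrast is significant 5% of the time.

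**Step 4: splitting the gap.** For the building effect at r = 0.5, moving from the interaction to a Week 6 change contrast takes power from 57% to 68%. Baseline adjustment takes it from 68% to 80%. About half of the gain is adjustment. For a sustained effect at r = 0.5 the interaction (70%) is no worse than the change contrast (68%), so adjustment supplies the whole advantage. An unadjusted Week 6 difference has 68% power at any r and would lose to the interaction test at r = 0.7 (68% against 80%).

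**Step 5: missing visits.** If 10% are missing independently at each follow-up visit, complete cases number 96 x 0.9² = 77.8, about 78. If the 10% is dropout that persists to Week 6, 96 x 0.9 = 86.4, about 86. For the sustained effect at r = 0.5, interaction power falls from 70% with 48 per arm to 60% with 39 per arm.

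**Step 6: two sets.** If a result is claimed when either PP or ITT is significant, and PP is a random 95% to 80% of ITT, the type I error per outcome is about 6.1% to 7.1%. This figure excludes any bias from selection.

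**The case against.** Several points on the other side stand.

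- The 2 df are derived, not stated. A mixed model with linear Time would give a 1-df slope test that an effect confined to Week 3 would not trigger. If only the two change scores are modelled, the interaction has 1 df and tests whether the Week 3 and Week 6 effects differ. It would then miss a constant effect and still flag a vanished one. This limits the figures to categorical Time, but it also shows that the sentence supports three different hypotheses.
- A reader might infer that the trial will be declared a success on a Week 3 effect. The documents contain no success rule, and the stated objective is exploratory. A Week 3 difference that fades is a true interaction, not a false positive.
- The end-point label in Section 3.5 sits beside those for the baseline and mid-term visits and may only mark the last visit.
- A reader might infer that the plan can produce no Week 6 estimate. Either model can give visit-specific estimates; what is missing is a designated contrast.
- A reader might infer that the ITT analysis will be one of completers, or that PP has priority because it is listed first. The first follows only if conventional repeated-measures ANOVA is chosen and visits are missed, and mixed models are equally permitted. List order shows nothing about the second.
- The power loss depends on correlation. At r = 0.8 it is 94% against 98%. With first-order autoregressive correlation of 0.7 and a flat effect, the interaction is slightly ahead (81% against 79%).

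None of these supplies a Week 6 contrast, a ranking of the sets or a rule for choosing the method.

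**Conclusion.** The point holds in conditional form. The only comparison stated for the primary outcomes is the Group by Time interaction, and it is not tied to Week 6. With categorical Time, compound symmetry, 48 per arm and r of 0.3 to 0.5, it is significant in about 55-70% of trials for a 0.5 SD effect that has vanished by Week 6, and equally often for one that persists. For a building effect it has about 43-57% power against 72-80% for a baseline-adjusted Week 6 contrast. That difference shrinks to 80% against 92% at r = 0.7 and is partly due to adjustment. All these figures rest on assumed effects and correlations; the missing link to Week 6 does not.

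The loss of incomplete participants (about 78 of 96 kept, at an assumed 10% missing per follow-up visit) applies only under the repeated-measures ANOVA option. The inflation from choosing between sets is modest.

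The documents do not support saying that the plan will declare success on a transient effect or that its ITT analysis is a completer analysis. They leave both open. The change should be made because it is cheap and gives a clearer answer at the last visit.

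**What to change.** In Section 4, remove repeated-measures ANOVA as an option. For each continuous primary outcome, state:

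- **Model.** A likelihood-based mixed model for repeated measures of the Week 3 and Week 6 values, with group, visit, group-by-visit, baseline value and baseline-by-visit as terms, or an equivalent constrained-baseline model.
- **Set.** All randomised participants with post-baseline data, analysed as allocated (ITT). PP is defined and used as a sensitivity analysis only.
- **Primary contrast.** The baseline-adjusted group difference at Week 6 with its 95% CI. The Week 3 difference and the overall Group by Time test are supportive.

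The baseline terms are essential: without them a Week 6 difference can have less power than the interaction test it replaces.

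Metagenomic and untargeted metabolomic data do not fit this model as they stand. They need their own method, or a named summary measure to which the model is applied.

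The cost is SAP wording, with no new visits, participants or measurements. The sponsor gives up the choice of method and set, and a transient Week 3 effect becomes a supportive finding.

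### Seven unranked primary domains are all tested at an unadjusted p < 0.05, so 5% is not the error rate for a positive primary result

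*Combined protocol and SAP*

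**What the plan says.** Section 3.6 lists seven primary outcome measures without ranking them. Section 4 carries all seven into one analysis sentence, "MPs, microbiota, metabolomics, inflammation, biochemistry, blood routine, and InBody data", and tests each over baseline, Week 3 and Week 6, "comparing the interaction between Group and Time. Significance level is set at" p < 0.05. That is the only threshold given.

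Most domains hold several variables:

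- **Fecal microplastics:** "Includes detection of 11 types of plastics (PC, PE, PP, PS, PA6, PET, PLA, PVC, PA66, PBAT, PMMA".
- **Microbiota:** "Assessed by Fecal Metagenomics sequencing to analyze diversity and functional genes", with no feature or index named.
- **Metabolomics:** untargeted, with no feature named.
- **Inflammation:** six named markers in a list left open, ending "P-selectin, CRP, etc".
- **Biochemistry:** four named lipids plus liver function tests that are not listed.
- **Blood count:** "Includes white blood cell count (WBC) and five-part differential".
- **Anthropometry and body composition:** six named measures.

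Neither the protocol sections nor the SAP section contains a multiplicity adjustment, a testing order, a summary variable for any domain, a deciding time point, false discovery rate control for the omics data, or a rule for how many outcomes must succeed.

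**The concern.** A significance level describes the trial's chance of a false claim only if the plan fixes which test supports the claim. Here any variable in any of seven domains, once below 0.05, could be reported as a positive primary outcome, and nothing in the text would contradict that. The error rate for the claim that the trial was positive on a primary outcome is then set by the number of tests and their correlation, not by the 5% in Section 4. Analysis after the fact cannot repair this, because choosing the decisive variable once results are known is the very problem that prespecification prevents.

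**Working it through.** **Inputs from the documents.** Alpha is 0.05 (Section 4; two-sided assumed, as sidedness is not stated). There are seven primary domains (Sections 3.6 and 4). There are 96 participants randomised 1:1 (Sections 3.2 and 3.4), so 48 per arm. The plan states no overall error rate or power figure that could be reproduced.

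**Count of named variables (Section 3.6).** 11 polymers + 6 serum markers + 4 lipids + 6 blood count variables (WBC and five fractions) + 6 anthropometric and body-composition measures = 33. The unlisted liver tests, further serum markers and both omics panels come on top.

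**Independent tests, no true effect.** The chance of at least one p < 0.05 among k tests is 1 − 0.95^k.

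- k = 7 (one test per domain): 1 − 0.698 = 30.2%.
- k = 33 (each named variable): 1 − 0.184 = 81.6%.
- Expected false positives at k = 33: 33 × 0.05 = 1.65, whatever the correlation.

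**Correlated tests.** The documents give no correlations, so all values here are assumptions. The figures come from 200,000 simulated sets of normal test statistics at two-sided 0.05.

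Seven tests, equal correlation r:

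| r | Chance of at least one false positive |
|---|---|
| 0 | 30% |
| 0.3 | 27% |
| 0.5 | 23% |
| 0.7 | 18% |

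Thirty-three tests, in blocks of 11, 6, 4, 6 and 6:

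| Within domain | Between domains | Chance of at least one false positive |
|---|---|---|
| 0.3 | 0 | 77% |
| 0.5 | 0 | 71% |
| 0.5 | 0.2 | 68% |
| 0.7 | 0 | 61% |
| 0.7 | 0.2 | 58% |
| 0.5 | 0.5 | 53% |
| 0.9 | 0 | 44% |
| 0.7 | 0.7 | 35% |
| 0.9 | 0.9 | 18% |

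The 33-test figures leave out the omics features. No figure counts the unranked choice between the PP and ITT sets, or between ANOVA and mixed models.

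**Cost of adjustment.** For a simple two-group t-test of means with 48 per arm, no dropout and 80% power, the detectable difference is 0.578 SD at alpha 0.05. At alpha 0.05/7 = 0.00714 it is 0.735 SD. (The normal approximation gives 0.57 and 0.72.) This is a yardstick only, because the planned test is a Group × Time interaction over three visits.

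**The case against.** A reader might infer that a positive primary result is likely, meaning more probable than not, even if the product does nothing. The documents do not support that without conditions. Section 4 names seven items and does not say that every component is tested separately. With one test per domain the figure is 23–30% at correlations of 0.5 to 0. The microplastics entry could also be read as one total, leaving 33 − 11 + 1 = 23 named variables and 1 − 0.95^23 = 69% under independence. Some variables are closely linked, such as weight with BMI or WBC with its differential, and strong enough correlation takes even 33 tests below one half. These limits stand. They reduce the size of the inflation but do not remove it: in every row above the rate exceeds 5%. Since no domain has a defined summary, testing variable by variable remains a natural reading.

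The second objection is that the trial is exploratory, since the Section 2 objective is framed as exploring a question. That partly stands, and an explicit exploratory label would be a legitimate remedy. However, Section 1 speaks of evaluating efficacy, the design is randomised, double-blind and placebo-controlled, and the outcomes are called primary and given a significance threshold. The current text does not settle which is meant.

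A reader might also infer that fecal microplastics is the lead outcome because it is listed first. Section 3.6 implies no ranking. The Section 2 objective concerns obesity-related adverse effects, and the documents do not say whether benefit means more or less microplastic in faeces.

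**Conclusion.** The concern holds, and the plan should be changed. As written, 5% is the error rate of each test and not of a positive primary result. With no true effect, the chance of at least one false-positive primary is about 30% for one independent test per domain and 23% at r = 0.5. If the 33 named variables are tested singly, it is 82% under independence, about 58–77% with within-domain correlation of 0.3–0.7 and between-domain correlation of 0–0.2, and 35% at 0.7 throughout. The counts and the absence of any control come straight from the text. The correlations are assumed, and the number of tests actually intended is not stated. Omics features would raise the figures.

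**What to change.** Amend Sections 3.6 and 4 before any unblinded data are seen. The documents do not give the trial's status; if results are already known, choosing a primary now would itself be post hoc and should be reported as such.

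1. **Preferred:** the sponsor names one primary variable at one time point, chosen for its link to the Section 2 objective, and states the direction of benefit. All other variables become secondary or exploratory and are reported with confidence intervals.
2. **Alternative:** keep one predefined variable per domain, including one predefined summary for each omics panel, and apply Holm at an overall 0.05.
3. **In either case:** control the false discovery rate within the metagenomic and metabolomic feature analyses.
4. **If the trial is meant to be exploratory:** say so, and make no confirmatory claim from any single p < 0.05.

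The cost is wording, with no new data or participants. Under option 1 most variables lose primary status. Under option 2 power falls: a seven-way Bonferroni bound raises the detectable difference from about 0.58 to 0.74 SD on the simple two-group yardstick, and Holm costs no more than that.
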